8.3 Device Usage Specification

After obtaining approval from the Ethics Committee, the Sponsor shall be responsible for providing the investigational medical devices to the clinical trial institutions and investigators, and determining the transportation conditions, storage conditions, storage duration, shelf life, etc.

The investigational medical devices shall be qualified in quality, with easy identification, proper coding, and affixed with the special label “For Clinical Trial Use Only”. They shall be properly packaged and stored in accordance with the requirements of the clinical trial protocol.

The Sponsor shall be responsible for the safety of the investigational medical devices during the clinical trial. When the Sponsor becomes aware of any issues that may affect the safety of subjects or that may alter the Ethics Committee’s approval for the continuation of the trial, it shall immediately notify all clinical trial institutions and investigators and take appropriate measures.

8.4. Monitoring Plan

In accordance with the requirements of the Medical Device Clinical Trial Quality Management Regulations, the sponsor will select inspectors who meet relevant requirements to perform inspection duties at all participating institutions. The number of supervisors and the frequency of supervision will be confirmed with the supervisor in accordance with the specific visit requirements and test procedures. Specific responsibilities shall include:

- 1) Confirm prior to the trial that clinical trial institutions are sufficiently equipped, including staffing and training, laboratories are fully equipped and in good working condition, there are enough subjects to participate in the trial and researchers are familiar with the trial requirements;
- 2) Monitor clinical trial institutions and researchers before, during, and after the trial to determine whether or not they are compliant with relevant regulations, the Medical Device Clinical Trial Quality Management Regulations and the clinical trial protocol;

- 3) Confirm that each subject signs an informed consent form prior to participating in the clinical trial, and understands the state of subject enrollment and trial progress; ascertain and record instances of failure to follow-up, perform testing or perform examinations by the investigators as well as whether or not such errors were subject to correction; and ensure that patients who have yet to complete the trial procedure and who are affected by revisions to the informed consent form re-sign the form;
- 4) Confirm that all case report forms are correctly filled out and consistent with the original data; all errors or omissions have been corrected or noted, and signed and dated by the investigator; and the disease type, total number of cases and the gender, age, and treatment efficacy pertaining to each case are confirmed and recorded;
- 5) Confirm that subject withdrawal from the clinical trial or failure to comply with the requirements specified in the informed consent form are recorded, and discusses the situation with an investigator;
- 6) Confirm that all adverse events, complications and device defects are recorded, and serious adverse events and device defects that may cause serious adverse events are reported and recorded by the appropriate deadlines;
- 7) Monitor the provision, use, maintenance, transportation, receipt, storage, distribution, processing, and recycling of trial medical devices;
- 8) Supervise regular maintenance and calibration of related equipment during the clinical trial;
- 9) Ensure that all clinical trial related documents received by investigators are current;
- 10) The monitor should issue a written report to the sponsor after each monitoring session; the report shall include the name of the monitor, the date of the monitoring session, the time of the monitoring session, the location of the monitoring session, the content of the monitoring session, the names of any related investigators, the completion status of the project, existing problems, a conclusion, and corrections, etc. to any errors or omissions.

9. Statistical Considerations

9.1. Sample Size Calculation

9.1.1. Total Sample Size

After accounting for a 20% dropout rate, the total sample size is determined to be 90 subjects. The sample size calculation formula is presented below:

$$n = \frac{\left[Z_{1-\alpha/2} \sqrt{P_0(1-P_0)} + Z_{1-\beta} \sqrt{P_T(1-P_T)} \right]^2}{(P_T - P_0)^2}$$

Where: P_T denotes the expected event rate of the investigational device, and P_0 denotes the objective performance criterion.

9.1.2. Number of Clinical Trial Subjects per Disease and Basis for the Determination Thereof

This study does not address issues of multimorbidity, so only the total number of clinical trial subjects is subject to requirements.

9.1.3. Minimum and Maximum Number of Subjects per Clinical Trial Institution and Corresponding Reasoning

This trial will be conducted simultaneously at multiple qualified clinical trial institutions in China. In principle, the number of enrolled subjects will be distributed as evenly as possible across each center to ensure sufficient center representativeness. However, considering feasibility and enrollment progress, adjustments to the number of enrollments will be made based on actual conditions to maintain a relatively balanced enrollment size per center. The final enrollment size of any given single center shall not exceed 50% of the total number of subjects.

9.2. Analysis Sets

The trial's statistical analysis will be conducted on the basis of the following analyzed populations,

which need to be clearly defined before the statistical analysis begins, and in this trial they include:

1. Full Analysis Set (FAS): Refers to the subject set that is as close as possible to intention-to-treat (ITT) principles, which is derived from all randomized subjects with minimal and reasonable censoring, and contains all subjects who have been subject to randomization and have previously used an investigational device. The FAS will be used for the evaluation of primary and secondary indicators.

2. Per Protocol Set (PPS): All patients showing good compliance with the trial protocol, good adherence, completion of the treatment specified in the trial protocol and no deficiencies in key efficacy indicators. The PPS will be used for the evaluation of primary and secondary indicators.

3. Safety Set (SS): All subjects who used an investigational device following randomization and underwent a safety evaluation. The SS will be is used for an analysis of safety indices.

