4.2. Content

This study will be conducted at qualified clinical research institutions. Investigators will perform endovascular treatment in patients with aortic arch lesions using the WeFlow-Tribranch embedded aortic Triple-branch arch Stent Graft system, developed and manufactured by Hangzhou Endonom Medtech Co.; Ltd. This is a prospective, multicenter, single-arm objective performance criterion clinical study. An internet-based registration system

will be used to enroll and document all study subjects. The study is planned to initiate in October 2023, with completion of 90 clinical implantations by December 2025. Clinical follow-up assessments will be performed before discharge, at 30 days, 6 months, 12 months, 24 months, 36 months, 48 months, and 60 months postoperatively. Computed Tomography Angiography (CTA) imaging follow-up will be conducted at 30 days, 6 months, 12 months, 24 months, 36 months, 48 months, and 60 months after the procedure.

The primary endpoint of this trial is the incidence of all-cause death or major stroke within 12 months after surgery. Effectiveness endpoints include the incidence of Type I or Type III endoleak, the incidence of aortic stent graft migration, postoperative branch vessel patency rate, and the rate of conversion to open thoracic surgery or secondary interventional procedures. Safety endpoints comprise all-cause mortality rate, aortic aneurysm-related mortality rate, the incidence of Serious Adverse Events (SAEs), and the incidence of device-related adverse events. After completion of the 12-month primary endpoint evaluation, the sponsor will finalize the clinical study report and submit it to the National Medical Products Administration (NMPA). Annual long-term follow-up will continue up to the fifth year to evaluate long-term clinical outcomes.

5. Background Information Pertaining to the Clinical Trial

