8.1.2. Trial Methodology and Rationale

This trial is designed as a prospective, multicenter, single-arm objective performance criterion clinical study.

Multicenter design: The trial will be conducted at multiple qualified domestic clinical centers. A multicenter approach facilitates patient enrollment, promotes benign competition among sites, and accelerates achievement of enrollment objective performance criterion. In addition, since subject data are collected from different regions and multiple centers by independent investigators, the final conclusions will be broadly representative.

Single-arm objective performance criterion design: Endovascular repair has become the preferred treatment for Stanford Type B thoracic aortic dissection; however, the management of lesions involving the ascending aorta or aortic arch remains challenging. Open surgery is the standard treatment for such diseases, yet it is associated with substantial surgical trauma, deep hypothermic circulatory arrest, antegrade/retrograde cerebral perfusion, and significantly elevated perioperative mortality and stroke rates. Patients enrolled in this trial generally present with aortic arch disease, advanced age, severe comorbidities, and are defined as high-risk individuals unsuitable for open surgery. Although existing thoracic aortic endovascular products can be modified and used off-label for aortic arch lesions, such structural adjustments lack adequate validation and carry potential safety and efficacy risks. Furthermore, no commercially available domestic device enables dual- or triple-branch reconstruction for supra-aortic arch vessels. Conservative medical treatment yields limited efficacy, and a more proactive intervention strategy is recommended for patients meeting intervention criteria. Setting a medical therapy control group would result in an extreme imbalance in risk–benefit profiles between the two arms. Therefore, a single-arm objective performance criterion design is adopted in this trial: a clinically meaningful objective performance criterion is predefined, and the safety and efficacy of the investigational device are evaluated without a parallel control group. The Guidelines for Clinical Trials of Transcatheter Implantable Artificial Aortic Valves issued by the NMPA recommend selecting clinically meaningful primary endpoints, with the 12-month cumulative all-cause mortality commonly proposed for sample-size estimation.

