- Concomitant medication records: medications relevant to the evaluation of the investigational device (including anticoagulants, antiplatelet agents, antihypertensives, lipid-lowering drugs, hypoglycemic drugs, antibiotics, etc.); and medications administered for underlying diseases, concomitant diseases, or adverse events.
- Adverse event records: all adverse events starting from Visit V2.
- In the event of a stroke in a subject, the modified Rankin Scale (mRS) score shall be collected at 90 days after the stroke onset.
- If feasible, laboratory data obtained within 15 days prior to subject enrollment (before signing the informed consent form), as well as aortic CTA, cerebral CTA or Magnetic Resonance Angiography (MRA), echocardiography, and 12-lead ECG data obtained within 30 days prior to signing the informed consent form, may be used for baseline assessment without repeat testing.
- Long-term follow-up CTA data shall be collected at postoperative Years 2, 3, 4 and 5 (± 30 days), with records of adverse events and concomitant medications related to adverse events.*Relevant examinations and data collection shall be performed only in patients randomized to the test group.

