9.4. Statistical Design, Methodology and Analytical Procedures

9.4.1. Statistical Design

This clinical trial adopts a prospective, multi-center, superiority, randomized controlled trial design to evaluate the efficacy and safety of the investigational device.

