9.4.2. Statistical Methodology and Analysis

1) General Principles

For quantitative variables, mean, standard deviation, median, minimum, maximum, lower quartile (Q1), and upper quartile (Q3) will be calculated. For categorical variables, the number and percentage of subjects in each category will be presented.

Comparison of general characteristics between the two groups will be analyzed using appropriate methods according to the type of variables. Between-group comparisons of quantitative data will be performed using the independent samples t-test (for homogeneous variance and normal distribution) or the Wilcoxon rank-sum test, depending on the data distribution. Categorical data will be analyzed using the chi-square test or Fisher's exact test (if the chi-square test is not applicable). Ordinal data will be analyzed using the Wilcoxon rank-sum test or the CMH test.

2) Completion Status and Demographic Analysis

The number of enrollments and completions for each center will be summarized and a list of fallout cases as well as a detailed list of reasons for non-completion will be created. Patients' demographic characteristics (age, sex, etc.), relevant medical history treatment, etc. will be described. A demographic analysis will be performed based on an FAS analysis set.

3) Primary Endpoints

Primary Endpoint: The incidence of all-cause death or major stroke within 12 months after the procedure. All-cause death includes cardiac death, non-cardiac death, and death of unknown cause. Major stroke is defined as a modified Rankin Scale (mRS) score ≥ 2 assessed at 90 days after stroke onset. The hypothesis testing is specified as follows:

Null Hypothesis: $H_0: P_T - P_C \leq \Delta$

Alternative Hypothesis: $H_1: P_T - P_C > \Delta$

$\alpha = 0.025$ (single tail)

At the significance level of $\alpha = 0.025$ (one-sided) and statistical power of $1 - \beta = 0.8$, the incidence rate of all-cause mortality or major stroke within 12 months post-procedure shall be statistically described, and its two-sided 95% confidence interval (95% CI) shall be estimated. The upper limit of the 95% CI

shall be compared with the Objective Performance Criteria (OPC). Statistical conclusions will then be drawn accordingly. If the upper limit of the 95% CI is lower than the objective performance criterion P_0 , the primary endpoint shall meet the trial requirements, and the investigational device can be considered to satisfy the requirements for clinical application.

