Missing data not attributable to unsatisfactory efficacy: loss to follow-up, failure to complete assessments, or other reasons such as force majeure (e.g., epidemic restrictions) resulting from adverse events, death, etc., unrelated to the investigational device or aortic dissection.

For the first category of missing data, worst-case imputation shall be used in both the FAS and Per Protocol Set (PPS), treated as “12-month postoperative failure”. For the second category of missing data, three imputation methods shall be applied separately, followed by sensitivity analysis:

1) Best-case imputation: all treated as “12-month postoperative success”; 2) Worst-case imputation: all treated as “12-month postoperative failure”; 3) Tipping-point analysis: the imputation proportions of success and failure in the two groups shall be varied iteratively to comprehensively demonstrate whether the study meets the statistical hypothesis under different scenarios and to identify the tipping point at which the conclusion changes.

No statistical imputation shall be used for missing data of other endpoints.

(2) Handling of inconsistent data: During data management, logical checks shall be performed on the database. Inconsistent data shall be queried via data query forms sent to investigators. Inconsistent data shall be resolved based on written responses from investigators. The database shall not be locked until all inconsistent data has been resolved.

(3) Handling of erroneous data: During data management, quality control should be conducted on the database. Erroneous data shall be identified and queried via data queries (Query). Errors shall be corrected based on investigators' responses, and queries shall be closed only after confirmation from investigators. The database shall not be locked until all erroneous data has been corrected.

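### Section 9 mixes randomised two-group text into a single-arm performance-criterion study, including the conditions for entering the Full Analysis Set and Safety Set

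*Protocol*

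**What the plan says.** Two descriptions of the trial stand in the same protocol version.

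**Single-arm.** Section 4.2: "This is a prospective, multicenter, single-arm objective performance criterion clinical study". Section 8.1.2 repeats it ("This trial is designed as a prospective, multicenter, single-arm objective performance criterion clinical study") and explains why there is no parallel control group. The bias measures listed before section 8.1.3 have patients entered one after another at each centre and registered. Section 8.2 goes from consent through screening and enrolment to surgery with no allocation step. No ratio, randomisation method or comparator appears anywhere.

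**Randomised, two groups.**
- Section 9.4.1: "This clinical trial adopts a prospective, multi-center, superiority, randomized controlled trial design".
- Section 9.2, FAS: it "contains all subjects who have been subject to randomization and have previously used an investigational device".
- Section 9.2, Safety Set: "All subjects who used an investigational device following randomization and underwent a safety evaluation".
- Section 9.4.2, general principles: "Comparison of general characteristics between the two groups", by t-test, Wilcoxon, chi-square, Fisher or CMH test.
- Section 9.4.2, primary endpoint: the hypotheses are written on P_T − P_C against a margin Δ.
- Section 9.5, tipping-point analysis: "the imputation proportions of success and failure in the two groups shall be varied iteratively".
- Section 8.2.1, notes to the chart: "Relevant examinations and data collection shall be performed only in patients randomized to the test group".

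**The concern.** The FAS is the set named for the primary and secondary endpoints, and the Safety Set is the main set for the secondary safety endpoints. Both are defined by an event that does not happen in this study. The Per Protocol Set does not mention randomisation, but it requires completed treatment and complete key efficacy data, so it cannot stand in for the FAS.

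An analyst must therefore depart from the text to obtain any FAS, and the protocol does not say in one place what the replacement is. In a single-arm study no second arm shares a change of denominator, so the choice of population acts directly on the confidence limit that is compared with the OPC. That choice should be written down before outcomes are known.

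A statistical analysis plan (SAP) cannot resolve this alone. If it follows the protocol it inherits the error, and if it departs from it the two documents disagree.

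**Working it through.** **1. The plan's own sample size.** Section 8.1.4.8 gives 72 evaluable subjects and 20% dropout: 72/(1 − 0.20) = 90. The stated total reproduces. The 72 itself cannot be recomputed, because the values of P_0 and P_T are redacted.

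**2. Which design that size belongs to.** The formula in section 9.1.1 is one-sample, with P_0 defined as the OPC:

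n = [z(1−α/2)·√(P_0(1−P_0)) + z(1−β)·√(P_T(1−P_T))]² / (P_T − P_0)²

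To show that a two-group reading does not fit, take one assumed pair that gives 72 at one-sided α = 0.025 and power 0.80: P_0 = 0.35, P_T = 0.20.
- One-sample: (1.960·√0.2275 + 0.8416·√0.16)² / 0.15² = 71.9, so 72.
- Two groups, 1:1, same rates: (1.960·√(2·0.275·0.725) + 0.8416·√(0.2275 + 0.16))² / 0.15² = 137.9, so 138 per arm and 276 in total.
- 72 evaluable subjects split 36/36 would have power of about 29%.

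Other assumed pairs also give 72 (for example 0.20/0.08 or 0.28/0.141). The rates serve only as illustration; the form of the formula already shows that 90 is a single-arm size.

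**3. The analysis sets read literally.** Subjects randomised = 0. The FAS requires randomisation and device use, so FAS = 0 of 90. The Safety Set requires device use after randomisation, so SS = 0 of 90.

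**4. Section 9, element by element.**

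| Element | Place | Form |
|---|---|---|
| Sample-size formula, N = 90 | 9.1.1 | single-arm |
| FAS and Safety Set | 9.2 | randomised |
| Design statement | 9.4.1 | randomised, controlled |
| Baseline tests | 9.4.2 | two-group |
| Hypotheses on P_T − P_C against Δ | 9.4.2 | two-group |
| Upper 95% limit below P_0 | 9.4.2 | single-arm |
| Tipping-point analysis | 9.5 | two-group |

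The hypotheses and the decision rule sit in the same subsection and do not match. P_C and Δ have no counterpart in the rule. The alternative also points to a larger event rate, while success under the rule is a smaller one.

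**5. What the denominator can do (assumed counts).** Suppose 17 of 90 subjects have an event, and 3 of those 17 had an attempted but failed implantation and are left out. With Clopper-Pearson limits (the protocol names no interval method):
- 17/90 = 18.9%, upper limit 28.5%.
- 14/87 = 16.1%, upper limit 25.5%.

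The deciding limit moves by 28.5 − 25.5 = 3.0 points. Whether such a shift would change the conclusion cannot be shown without P_0.

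**The case against.** The best defence is that this is leftover template wording that no competent analyst would apply. The study's nature is plain from sections 4.2 and 8.1.2, and the test that decides the trial, an upper limit against P_0, needs no second group. The two-group instructions that remain concern baseline description and a sensitivity analysis. Striking the randomisation condition leaves a usable FAS: close to intention to treat, and device used. That agrees broadly with the treated-subjects denominator in section 8.1.5. Superiority is not wrong in itself either, since beating an OPC is a superiority claim.

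Much of this stands. A reader might infer more than the text supports in four ways:
- **That the primary analysis cannot be run.** It can, once the FAS is restated.
- **That failed implantations would be left out.** Section 8.1.6 makes technical success a secondary efficacy endpoint, and section 9.4.2 analyses those endpoints in the FAS. The rate means little unless failures are in that set. Section 8.1.4.3 also keeps data on all enrolled subjects for an intention-to-treat analysis.
- **That the sets would be settled after the data are seen.** Section 9.2 requires them to be defined before analysis begins, and section 9.5 requires a SAP before the study starts.
- **That the chart note restricts data collection generally.** It is tied to an asterisk, and no row of the chart as reproduced carries one.

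The defence does not show that the text may stay. The wording recurs in sections 8.2.1, 9.2, 9.4.1, 9.4.2 and 9.5 and reaches the definition of the primary population. The candidate replacements also differ: treated subjects (8.1.5), subjects who used the device (9.2), and the enrolled subjects whose data are kept for intention to treat (8.1.4.3). Section 9.3 further allows elimination from the analysis sets without exempting the FAS, with never having used the device as one example. None of these says outright whether an attempted but undeployed implantation counts.

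**Conclusion.** The point holds as a contradiction that must be corrected. The stated design, two of the three analysis sets, the written hypotheses, the baseline tests and the tipping-point analysis belong to a randomised two-group trial, and this study is not one. Read literally, the FAS and Safety Set contain 0 of 90 subjects. That measures how wrong the wording is; it does not predict what would be analysed.

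The one-sample formula, the comparison of the upper limit with P_0 and N = 90 are unaffected. The 3.0-point shift in the limit rests on assumed event counts and an assumed interval method. It shows only that the population needs fixing in advance. The protocol gives no outcomes by failed or aborted implantation, so nothing can be said about whether deaths and strokes would gather there.

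**What to change.** - **9.4.1:** state a prospective, multicentre, single-arm trial compared with an OPC.
- **9.2:** define the FAS and Safety Set without randomisation, as all enrolled subjects in whom implantation of the investigational device was attempted, whether or not it was deployed. This fits the intention-to-treat wording in 9.2, the denominator in 8.1.5 and the technical-success endpoint in 8.1.6. Use the same wording for the denominator in 8.1.5.
- **9.4.2, hypotheses:** H0: P_T ≥ P_0 against H1: P_T < P_0, matching the existing decision rule.
- **9.4.2, general principles:** delete the between-group tests and keep the descriptive statistics.
- **9.5:** make the tipping-point analysis one-group, counting from none to all of the subjects with missing outcomes in the second category as events, and report where the conclusion changes.
- **8.2.1:** remove the note on patients randomised to a test group, or reconcile it with the single-arm design.

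Cost: a protocol amendment with ethics committee approval (sections 13.2 and 15.3) and matching SAP wording. The sample size does not change and no extra data are needed. It should be done before outcome data are reviewed.
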